## **Study Protocol**

The purpose of this project is to assess a self-paced online program, *Media Aware Parent: Tween (MAP: Tween)*, designed to provide parents with knowledge about preadolescent development, media mediation skills, and practice in high-quality parent-child communication about body image, sexual development, gender stereotypes, and romantic relationships. The program will help parents of preadolescents (9-12 years of age) have effective conversations with their child about these topics and enhance media literacy skills to counter unhealthy media messages.

Study participants will contribute to the evaluation of a web-based application that will act as a resource for parents to have informed high-quality conversations with their preadolescent child about body image, sexual development, gender stereotypes, and romantic relationships. Through their participation, parents and children in the study may also acquire an increased knowledge about these topics and media literacy.

Preadolescence is a critical stage of development as youth transition from childhood into adolescence, and the *MAP: Tween* program may help improve communication between parents and children. High-quality parent-child communication has been shown to positively impact youth decision-making and health outcomes; therefore, this program has the potential to benefit society by resulting in an evidence-based program to enhance parent-child communication.

The procedure that will be used for conducting the research study is as follows:

1. We will aim to recruit a diverse sample of 300 parent-tween pairs (youth aged 9-12) to participate in this study. We will aim to have the sample consist of at least 40% fathers or male guardians and no more than 60% non-Hispanic/Latinx white adult participants. Parent-child pairs will be stratified by parent's gender and race/ethnicity prior to randomization to ensure diversity across groups.
2. A recruitment website will be available. Interested parents can complete an online screener found on the website. If eligible, parents will be directed to a place where parents and their children can complete the online informed consent process.
3. On the parent permission and consent form, participants will be asked for their preferred email address to receive study communications over the study period. Before receiving communications at this address, they will need to verify that they can receive emails at this address by clicking a link that is emailed to them. Parents will also be asked on the permission and consent form to agree to receiving study communication via text. Before receiving text communications at their phone number, they will need to verify that they can receive texts at their number by clicking on the verification link that is sent via SMS message. Finally, parents will also be asked to verify their name and address either through uploading on the permission-consent form an image of some form of document that includes their name and address (e.g., license; electric bill) or showing the document to a study team member through a live web conferencing call (e.g., Zoom call). [Modification: Due to concerns of people uploading images of documentation that was photoshopped, during the study the verification protocol was modified (and approved by the IRB) so that all participants were asked in the screener survey to indicate the school district where their

child attended school and then this was checked against our list of schools that distributed our flyer. Only parents that listed a school district where our flyer was distributed, were enrolled.]

4. The study team will enroll eligible, consented, and verified pairs based on whether there is room in the study according to gender and race/ethnicity stratification. If there is space in the study, parent-child pairs will be randomly assigned to either the Intervention condition (receiving the *MAP: Tween* program) or the Active Control condition (i.e., receiving medically-accurate information from sources like the CDC about topics such as preadolescent development, body-image, gender, and relationship health).
5. Pretest questionnaires for parents and their children will be distributed to enrolled parents in two separate emails/texts containing a link to complete their respective questionnaires. Participants will have one week to complete their questionnaires. If both the parent and child complete their questionnaire, they will be eligible for a \$30 gift card.
6. Parents will receive a reminder (email, phone call, or text) to complete the pretest questionnaires if both are not completed in the first two business days. If both questionnaires are not completed, the parent will receive a final reminder around the 6th day.
7. Once pretests questionnaires are completed, parents will receive a link to access their randomly assigned resource (i.e., *MAP: Tween* OR medically-accurate information from sources like the CDC). The resources could take up to a total of 2 hours to review over the course of 3 weeks. Parents who complete the program within 3 weeks will be eligible to take the parent feedback questionnaire. Completion of the feedback questionnaire may take up to 15 minutes. If the parent completes the questionnaire, they will be eligible for a \$40 gift card.
8. About four weeks after pretest questionnaire completion, parents will receive two emails/texts – one with a link to their posttest questionnaire and one with a link to their child's posttest questionnaire. Participants will have one week to complete their questionnaires. If both the parent and child complete their questionnaire, they will be eligible for a \$45 gift card. Parents will receive a reminder (email, phone call, or text) to complete the posttest questionnaires if both are not completed in the first two business days. If both questionnaires are not completed, the parent will receive a final reminder around the 6th day.
9. Incentives will take the form of gift cards. Participants will be emailed the appropriate Amazon.com electronic gift card after completing the study questionnaires.

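### Pairs are randomized before the pretest, yet access and posttest depend on completing it, so the intent-to-treat analysis in practice covers pretest completers; assigning the arm when the link is sent is a cheap improvement

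*Combined protocol and SAP*

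**What the plan says.** The Study Protocol fixes the order of events.

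- Step 1 sets the target, "We will aim to recruit a diverse sample of 300 parent-tween pairs", and stratifies by parent gender and "race/ethnicity prior to randomization to ensure diversity across groups".
- Step 4 makes the assignment: "If there is space in the study, parent-child pairs will be randomly assigned to either the Intervention condition" or to the active control.
- Step 5 follows: "Pretest questionnaires for parents and their children will be distributed to enrolled parents in two separate emails/texts". The pair has one week to reply.
- Step 6 adds a reminder by email, phone or text "to complete the pretest questionnaires if both are not completed in the first two business days", and a last one near the end of the week.
- Step 7 opens access: "Once pretests questionnaires are completed, parents will receive a link to access their randomly assigned resource".
- Step 8 dates the outcome: "About four weeks after pretest questionnaire completion, parents will receive two emails/texts", with links to the two posttests.

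No step says what happens to a randomized pair whose pretests are not both completed. No step says whether families, or the staff who send reminders, know the arm during the pretest week.

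In the SAP, Main Analyses promises intent-to-treat regressions of posttest on pretest, arm and covariates. The covariates include supportive parenting as reported by the parent and by the child. Preliminary Analyses plans multiple imputation pooled by Rubin's Rules and checks group balance on pretest characteristics. Neither section defines the intent-to-treat set.

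The modification noted in step 3 is in the past tense ("Only parents that listed a school district where our flyer was distributed, were enrolled"), so some or all of the randomization may already have been done.

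**The concern.** Randomization creates the groups to be compared, and an intent-to-treat analysis is meant to follow every pair in them. Here a pair can be randomized and then reach a point beyond which nothing is provided and nothing is measured. That pair lacks the outcome and at least one pretest questionnaire. The balance check does not cover it fully either, because it uses pretest data.

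Two things are at stake. The first is what the result describes: all randomized pairs, as the label says, or only those who completed the pretest. Two analysts could follow this SAP and analyse different sets. The second is that an arm exists while the pretest is answered and reminders are sent. If anyone involved knows it, completion of the pretest, or the pretest answers later used as covariates, could differ by arm.

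**Working it through.** **Inputs.** From the documents: 300 pairs, the order of steps 4 to 8, and the regression model. Not in the documents, so assumed: pretest non-completion f of 5–20%, 1:1 allocation, pre/post correlation r = 0.6 (0.4–0.8 where a range is shown), outcomes in SD units, no further loss at posttest. The plan gives no completion rate, effect size or power calculation, so there is no figure of its own to reproduce.

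**1. What each randomized pair has**

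| | Both pretests completed | Not both completed |
|---|---|---|
| Arm (step 4) | yes | yes |
| Access to the resource (step 7) | yes | none described |
| Posttest date (step 8) | yes | none described |
| Pretest scores and covariates for the model | yes | at least one questionnaire missing |

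**2. Number of pairs in the right-hand column.** 300 × f = 15 (5%), 30 (10%), 60 (20%).

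**3. Precision.** SE of the adjusted effect in completers = 2√(1 − r²) / √(300(1 − f)). At r = 0.6 the numerator is 2 × 0.8 = 1.6:

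- f = 5%: 1.6/√285 = 0.0948
- f = 10%: 1.6/√270 = 0.0974
- f = 20%: 1.6/√240 = 0.1033

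The formula contains the number of completers but not the time of assignment, so the order of steps does not change the SE.

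**4. What imputation adds.** A simulation used 1,500 runs, 300 pairs, r = 0.6, 30 imputations and Rubin's Rules. The true effect was 0.30 SD in completers and 0 in pairs without access, and non-completion was unrelated to arm. Non-completers had no posttest, and 0, 50 or 100% of their own pretests were known.

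- f = 20%: SE 0.1034/0.1035/0.1035 for completers alone, and 0.1039/0.1041/0.1039 after imputing everyone with arm in the model. The imputed estimate averages 0.300/0.297/0.298.
- f = 5%: SE 0.0949/0.0948/0.0950 against 0.0950/0.0950/0.0952.

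The average effect over all randomized pairs at f = 20% is 0.8 × 0.30 = 0.24 under these assumptions. Imputation with arm in the model returns about 0.30 instead: the completers' effect, credited to pairs that had no access.

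**5. Bias if the arm is known during the pretest**

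(a) Differential non-completion. Raw shift = (arm difference in non-completion) × (outcome gap of non-completers). With assumed values this runs from 0.05 × 0.2 = 0.01 to 0.10 × 0.5 = 0.05 SD. The planned model adjusts for pretest. If non-completion depends only on the pretest score, adjustment removes the shift. If it depends directly on the posttest score, a fraction 1 − r² = 0.64 remains: 0.05 × 0.64 = 0.032. A simulation with 10% against 20% non-completion and a gap near 0.5 SD agrees: raw 0.049 becomes 0.000 in the first case, and raw 0.051 becomes 0.033 in the second. The range at r = 0.6 is therefore about 0–0.03 SD.

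(b) Shifted pretest answers. An arm difference s in pretest answers that does not carry into the posttest moves the adjusted effect by r × s in the opposite direction: 0.6 × 0.1 = 0.06 SD (0.04 at r = 0.4, 0.08 at r = 0.8).

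At r = 0.6 both are below one SE. At r = 0.8 the SE is 1.2/√285 = 0.0711 to 1.2/√240 = 0.0775, so the 0.08 shift slightly exceeds it.

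**The case against.** Randomizing before baseline is accepted practice when the arm is concealed, and every trial with dropout fails to observe some randomized participants. The SAP does plan multiple imputation. The one-week window, the reminders and the gift card all work to keep non-completion low. Re-ordering would yield the same analysable pairs with the same SE, and one sentence defining the analysis set would make the label accurate. The re-ordering may also come too late.

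Much of this stands. The rate may be small, and the estimate applies to pretest completers in either order. But this loss differs from ordinary dropout: the plan itself withholds both access and posttest, and imputation cannot supply what was never scheduled. A sentence on the analysis set would settle the label, but it would not remove the period in which an arm exists while covariates are collected and reminder calls are made.

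A reader might infer that families learn their arm early and that the comparison is therefore biased. The documents do not support that: no arm-specific contact is described before the link in step 7, and silence on concealment is not evidence of disclosure. What staff know while sending reminders is simply unstated. A reader might also infer that early assignment wastes precision. It does not, for a given number of completers.

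**Conclusion.** The point holds as a cheap improvement, not as a fatal flaw. As written, an analysis labelled intent-to-treat estimates the effect in pairs that completed the pretest. How far that departs from all randomized pairs cannot be determined from the documents; the 15–60 pairs rest wholly on the assumed 5–20%.

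With concealment until the link is sent, this step contributes no bias to the completer comparison. Without it, the modest shifts worked out above apply. They depend on the assumed correlation, arm difference, outcome gap and pretest shift, none of which the documents give.

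**What to change.** **If assignment can still be moved.** Hold the quota place at enrolment, collect both pretests, and randomize within strata of parent gender by race/ethnicity immediately before sending the link. Release the place if the one-week window closes unfinished. The randomized set is then the intent-to-treat set: every pair in it has a pretest, access and a posttest date, and no arm exists while the pretest is under way. Imputation is then needed only for later losses.

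The cost is a change of protocol wording and of the moment of assignment. Step 7 already requires knowing that the pretests are complete, the strata are known at enrolment, and nothing in steps 5 and 6 depends on arm. The downside is that a place is tied up for about a week.

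**If randomization has already taken place.** Report pretest non-completion by arm, and whether the arm was concealed from families and reminder staff until pretest completion.

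- If it was concealed, make the main analysis the pairs with both pretests, analysed as assigned, and describe the result as applying to pretest completers.
- If it was not, do not treat the completer analysis as free of selection bias. Present it beside an analysis of all randomized pairs, including one that imputes non-completers without an arm effect. That version returns (1 − f) times the completers' effect by construction, so a smaller estimate from it is not in itself evidence of bias.

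This costs two reporting items, a definition of the analysis set and, without concealment, the additional analysis of all randomized pairs.

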## **Statistical Analysis Plan**

Preliminary Analyses. Psychometric analyses will be conducted to study the reliability, validity, and distributions of key variables. These analyses will be conducted by first assessing the internal consistency (i.e., Cronbach's alphas) of outcomes with Likert-type scales. If the alpha for an outcome is unacceptable (i.e., less than 0.70), then items that do not correlate strongly with the total scale will be removed, one-at-a-time, until the alpha for the scale is acceptable. Once items are averaged together to create the scale, outcome distributions will be assessed using univariate analyses to examine skewness and kurtosis, providing preliminary insight into potential deviations from normality prior to model fitting. If outcomes are unacceptably skewed or kurtotic, then outcomes scales will be modified (via re-scaling or dichotomizing) or eliminated

from analysis. The impact of random assignment on producing equivalent groups will be assessed on pretest demographic and background characteristics in a series of t-tests and  $\chi^2$  analyses. If we establish that the groups are not equivalent on any pre-specified variables, these variables will be used as covariates in the analyses of intervention effects. For continuous outcomes, normality assumptions will be tested using the Shapiro-Wilk test, Q-Q plots, and histogram of the residual distributions, via linear regression analyses of raw data, with all covariates included in the model. If the Shapiro-Wilk test is significant (p-value of  $w < .05$ ), the histogram of residuals deviates substantially from a bell curve, and the Q-Q plot includes a pronounced S-curve (deviates substantially from the line), then the outcome scale will be transformed (via re-scaling or dichotomizing) or eliminated from analyses. Finally, we will use multiple imputation to handle missing data and analyses will be conducted on each imputed dataset, with resulting estimates and standard errors pooled using Rubin's Rules.

**Main Analyses.** Analyses will examine the effects of the program on attitudes, cognitions, and behaviors, which will provide information on program feasibility. We will use a series of linear regressions for outcomes with continuous distributions and logistic regressions for dichotomous (yes/no) outcomes in intent-to-treat analyses. Posttest scores will be regressed onto pretest scores, covariates, and the intervention effect. Covariates will include those that were non-equivalent between groups at pretest, parent sex, child sex, socioeconomic status, and parent- and child-reported supportive parenting. The Benjamini-Hochberg procedure will be employed to control for the False Discovery Rate (FDR).

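### Extra covariates are chosen by between-arm baseline tests with no stated cut-off or list, and the stratifier race/ethnicity can enter the model only by that route

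*Combined protocol and SAP*

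**What the plan says.** The Main Analyses paragraph of the SAP sets the model: "Posttest scores will be regressed onto pretest scores, covariates, and the intervention effect". It then gives the covariates: "Covariates will include those that were non-equivalent between groups at pretest, parent sex, child sex, socioeconomic status, and parent- and child-reported supportive parenting". So there is a fixed part (pretest score, sex of parent and child, a socioeconomic measure, and supportive parenting as rated by each of them) and a conditional part.

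The Preliminary Analyses paragraph explains the conditional part. "The impact of random assignment on producing equivalent groups will be assessed on pretest demographic and background characteristics in a series of t-tests" (and chi-square tests), and then: "If we establish that the groups are not equivalent on any pre-specified variables, these variables will be used as covariates". The only p-value threshold in the SAP, .05, belongs to the Shapiro-Wilk test of residuals. That residual check is itself run "via linear regression analyses of raw data, with all covariates included in the model".

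In the Study Protocol, step 1 stratifies pairs by the parent's "gender and race/ethnicity prior to randomization to ensure diversity across groups". Step 4 enrolls pairs "based on whether there is room in the study according to gender and race/ethnicity stratification" and then assigns them at random. No blocking is described. Step 5 comes after assignment: "Pretest questionnaires for parents and their children will be distributed to enrolled parents".

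**The concern.** In a randomized trial a baseline difference between arms is mostly chance. Adjustment pays when a covariate predicts the outcome, and a between-arm test carries no information on that. There is one partial exception: the pretest follows assignment, so a difference could also reflect unequal pretest completion.

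Three things follow.

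- **The model is not known until the arms are compared.** With neither a cut-off nor a list in these documents, two analysts could follow the SAP and fit different models.
- **The rule works against the stratifier.** Parent gender is covered by parent sex in the core; race/ethnicity is not. The better the allocation balances race/ethnicity, the less likely the test is to select it.
- **The covariate set has other uses.** It determines which conditional odds ratio the logistic models estimate. It also feeds the residual check, which can lead to an outcome being transformed, dichotomized or dropped. The effect on that check has not been quantified.

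At stake are some precision and the credibility of pre-specification. Bias is not the issue.

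**Working it through.** The plan gives no figure to reproduce here: it states no effect size, power or randomization method. From the documents come the target of 300 pairs and the recruitment limits (at least 40% male parents, at most 60% non-Hispanic/Latinx white parents). Everything else is assumed: 1:1 allocation, an effect of 0.3 SD, a 60/40 race/ethnicity split, 40% male parents, and a test cut-off of 0.05 unless stated.

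**1. How often the model changes.** For k independent candidates tested at level a, the chance that at least one is flagged under sound randomization is 1 − (1 − a)^k.

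| Cut-off | k = 5 | k = 10 | k = 15 |
|---|---|---|---|
| 0.05 | 22.6% | 40.1% | 53.7% |
| 0.10 | 41.0% | 65.1% | 79.4% |

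These are not error rates. They show how far the final model depends on an unstated threshold and list.

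**2. Race/ethnicity left to the test.** Let r be its correlation with the outcome after core adjustment. The matching gap between groups is r/√(0.6 × 0.4), which is 0.20, 0.41 and 0.61 SD for r = 0.1, 0.2 and 0.3. The smaller values are more plausible. The simulation used 30,000 trials per cell, with parent gender in every model and a chi-square flag at 0.05.

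| | r = 0.1 | r = 0.2 | r = 0.3 |
|---|---|---|---|
| *Blocks of 4 within strata* (flagged in 0% of trials) | | | |
| Type I error, omitted | 4.71% | 4.43% | 3.96% |
| Power, omitted | 73.26% | 73.88% | 74.15% |
| Power, included | 73.66% | 75.03% | 77.23% |
| Power lost (points) | 0.4 | 1.2 | 3.1 |
| *Unblocked* (flagged in about 5%) | | | |
| Type I error, omitted | 4.93% | 5.19% | 4.98% |
| Type I error, two-step rule | 4.91% | 5.06% | 4.75% |
| Power, two-step rule | 73.14% | 73.98% | 73.28% |
| Power, included | 73.36% | 75.41% | 76.80% |
| Power lost (points) | 0.2 | 1.4 | 3.5 |

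A closed form confirms the blocked type I error. Balance removes the share r² from the variance of the estimated effect, but the reported standard error keeps it, so the true rejection rate is 2Φ(−1.96/√(1 − r²)). This gives 4.9%, 4.5% and 4.0%. The simulation error of one power estimate is √(0.74 × 0.26/30,000), about 0.25 points, so the losses at r = 0.1 are close to noise.

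**3. Several candidates.** Here 5 or 10 independent candidates each have r between 0.05 and 0.15, with 150 pairs per arm and 20,000 trials per cell.

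| Rule | Type I error, range over cells |
|---|---|
| Cut-off fixed at 0.05 | 4.4% to 5.2% |
| Smaller p-value of cut-offs 0.05 and 0.10 | 4.9% to 5.5% |
| Smallest p-value of no additions, 0.05, 0.10 and 0.20 | 5.4% to 6.7% |

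**4. Logistic outcomes.** With a control rate of 40% and a conditional odds ratio of 2.00, leaving out a normal covariate with odds ratio 1.2, 1.5 or 2.0 per SD and integrating over it gives 1.99, 1.95 or 1.87. This is non-collapsibility: the target changes, and no bias is involved.

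**The case against.** The strongest reply is that these numbers show little harm. With a cut-off fixed in advance, type I error is nominal or slightly low. At r = 0.1 to 0.2 the power loss is 0.2 to 1.4 points. The loss of 3.1 to 3.5 points needs a 0.61 SD gap that survives adjustment for the whole core. The 6.7% figure needs the best of four rules picked after outcomes are seen, and ten candidates that together explain 10 × 0.15² = 22.5% of residual variance. Nothing in the SAP suggests such picking; the tests sit under Preliminary Analyses and are limited to variables called pre-specified. All of this stands, and it is why the point is not graded as essential.

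Other objections stand in part:

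- A variable list may exist outside these documents. It would not by itself supply a cut-off or put race/ethnicity in the model.
- The covariate sentence need not be read as exhaustive, but it names no other route for race/ethnicity.
- The strata may serve as enrollment quotas with unblocked assignment. Omitting race/ethnicity then leaves type I error nominal, and the case for including it is precision alone.
- Under step 7 of the Study Protocol the assigned resource is released only after the pretest. Unequal pretest completion is therefore less likely, although the documents do not say whether families learn their arm sooner.
- The residual check requires three signs together, so one or two weak covariates would seldom change its result.
- Dropping baseline p-values is partly a reporting preference.

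**Conclusion.** The concern holds as a specification weakness of modest size. The SAP chooses its additional covariates on a criterion unrelated to prognosis and leaves the threshold and candidates unstated in these documents. It gives race/ethnicity no dependable place in the model although pairs are stratified on it.

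The likely cost is about 0 to 1.5 points of power, or up to 3.5 if race/ethnicity is strongly prognostic beyond the core. There is no type I inflation under a rule fixed in advance. A small inflation is possible if the cut-off were settled after outcomes were seen, which the wording does not exclude. If allocation is blocked within strata, omitting a prognostic stratifier makes the test slightly conservative. These sizes rest on the assumed effect, split, prognostic strengths and allocation methods. The reading of the text does not. The change should be made because it is better and nearly free.

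**What to change.** - Delete the test-then-adjust rule from both paragraphs of the SAP.
- Before any comparison of the arms, name one covariate set for every model: the existing core, parent race/ethnicity as stratified, and any other variable justified beforehand as prognostic. Use the same set in the residual check.
- Report baseline characteristics and pretest completion by arm descriptively, without p-values (a secondary point).
- Treat adjustment for an observed imbalance as a labelled sensitivity analysis.

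Step 3 of the Study Protocol describes a change made during the study in the past tense, so the arms may already have been compared. If so, disclose this, state the list and cut-off used, and report the fixed-set model alongside.

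The cost is SAP wording, since race/ethnicity is already collected for stratification, and a few degrees of freedom out of about 300. A chance imbalance outside the list would be addressed only in the sensitivity analysis. Additions should be few: with ten weak candidates (r = 0.05), including all of them gives 73.1% power against 73.4% under the two-step rule, so nothing is gained.

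### Both non-normality rules let an outcome be re-scaled, dichotomized or dropped with nothing to choose among them, although linear regression at this sample size needs neither of the last two

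*Combined protocol and SAP*

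**What the plan says.** The Statistical Analysis Plan, Preliminary Analyses, contains two rules triggered by the shape of an outcome.

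- **Univariate rule:** "If outcomes are unacceptably skewed or kurtotic, then outcomes scales will be modified (via re-scaling or dichotomizing) or eliminated". No limit for skewness or kurtosis is given.
- **Residual rule:** the raw data are fitted by linear regression with all covariates. The rule acts when Shapiro-Wilk is significant at .05 and, jointly, "the histogram of residuals deviates substantially from a bell curve, and the Q-Q plot includes a pronounced S-curve". Its consequence is "then the outcome scale will be transformed (via re-scaling or dichotomizing) or eliminated from analyses".

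Main Analyses then assigns the model by outcome type: "linear regressions for outcomes with continuous distributions and logistic regressions for dichotomous (yes/no) outcomes in intent-to-treat analyses". The model itself is "Posttest scores will be regressed onto pretest scores, covariates, and the intervention effect". These analyses have a stated use, "which will provide information on program feasibility", and Benjamini-Hochberg is applied across them.

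The plan does not rank the three responses, name a transformation, give a cut point, or say whether the pretest is split along with the posttest. It does not commit to reporting the untransformed result.

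**The concern.** Two careful analysts could treat the same outcome differently and both be following the plan. One takes a log, one splits the scale, one removes the outcome. The choice matters in three ways.

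- A split moves the outcome from linear to logistic regression, so the effect changes from a mean difference to an odds ratio.
- A split can discard information and therefore power.
- Elimination leaves the question unanswered and shrinks the Benjamini-Hochberg family.

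The residual rule cannot be applied until posttest scores exist, because they are the regression outcome. Nothing says the choice is made without sight of arm. The membership of the multiplicity family therefore depends on judgement exercised after the outcome data are in hand.

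Both rules also presume that non-normality is a serious problem for linear regression at this sample size. That presumption can be checked.

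**Working it through.** The documents give no power calculation, effect size or SD, so there is no stated figure to reproduce.

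**Inputs from the documents.** 300 pairs as a recruitment target (Study Protocol, step 1); two arms (step 4); averaged Likert-type scales (Preliminary Analyses); regression on arm, pretest, parent sex, child sex, socioeconomic status and two supportive-parenting scores (Main Analyses).

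**Assumptions.** 1:1 allocation, two-sided 0.05 per test, latent effect 0.3 SD, latent pretest-posttest correlation 0.6, five items scored 1 to 5 with loading 0.75. The split is at the pooled posttest cut nearest 50/50, analysed by logistic regression with a continuous pretest.

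**Analytic check: normal outcome, 150 per arm, d = 0.30, unadjusted.**

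- Continuous: power = Φ(d√(n/2) − 1.96) = Φ(0.30 × √75 − 1.96) = Φ(0.638) = 73.8%.
- Median split: proportions Φ(−0.15) = 0.440 and Φ(0.15) = 0.560, difference 0.119. Power = Φ[(0.1192 − 1.96 × 0.0577)/0.0573] = 54.2%.

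**Main simulation: n = 300, 4,000 trials per cell** (Monte Carlo SE about 0.35 points for type I error, 0.8 for power).

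| Raw skew under the null | -0.5 | -1.1 | -1.9 | -3.5 |
|---|---|---|---|---|
| Share at maximum score | 7% | 22% | 47% | 77% |
| Linear regression, type I error | 4.8% | 4.9% | 4.4% | 5.3% |
| Power, original scale | 75.9% | 70.0% | 56.2% | 35.2% |
| Power, reflected log | 75.8% | 72.2% | 59.0% | 37.6% |
| Power, median split | 55.2% | 52.8% | 47.4% | 36.0% |
| Split minus original, points | -20.7 | -17.2 | -8.8 | +0.8 |

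Splitting the pretest as well gives 53.6 / 51.9 / 46.4 / 35.9%.

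**Loss expressed as pairs.** Equivalent n = 300 × [(1.96 + z(power, split)) / (1.96 + z(power, original))]².

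- Skew -0.5: 300 × [(1.96 + 0.131)/(1.96 + 0.703)]² = 185.
- Skew -1.1: 300 × [(1.96 + 0.070)/(1.96 + 0.524)]² = 200.
- Skew -1.9: 300 × [(1.96 − 0.065)/(1.96 + 0.156)]² = 241.

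**With 20% loss (assumed), n = 240.** Type I error is 5.2 / 5.1 / 4.9 / 4.7%. Power on the original scale is 65.0 / 59.1 / 48.7 / 28.9%, against 45.5 / 44.4 / 41.4 / 28.7% for the split.

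**Different settings.** A separate simulation used a five-item, four-point scale, latent effect 0.38 and 2,000 trials per cell. At n = 300, power on the original scale against the split was 90.8 v 72.6% (skew -0.4), 86.8 v 70.5% (-0.8), 78.6 v 64.0% (-1.4) and 64.9 v 59.9% (-2.2). Type I error of linear regression was 4.9% to 6.2%. With unbounded skewed errors (residual skew 0 to 4.0, shift 0.28) it was 4.7% to 5.2%.

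**Does the numeric trigger discriminate?** At n = 300 Shapiro-Wilk rejected in about 88% of trials at a residual skew of only 0.5, and in all trials at about 1. In practice the two visual signs decide.

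**Side check on zero-heavy counts, n = 300.** The documents describe no count outcome, so this only tests reach. With 51% zeros, type I error was 5.0% and power 41.9% raw, 44.6% log(1+y), 29.0% any-versus-none. With 82% zeros, type I error was 5.4% and power 19.8 / 19.4 / 17.6%.

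**The case against.** The strongest reply has five parts.

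1. **The median split is not in the plan.** True. The power figures illustrate one possible cut and an assumed effect; they do not measure this plan. The missing cut point is itself part of the gap.
2. **The loss is largest where the rules are least likely to act.** This stands as a limit on size. Loss is greatest at mild skew, about 9 points at -1.9 and none at -3.5. The visual criteria that restrain the rule are, however, subjective.
3. **A split can win.** With a pure location shift and unbounded skewed errors, the split had more power than linear regression at residual skew 2.6 (88.1 v 81.4%) and 4.0 (95.3 v 81.5%). No such gain appeared for the bounded Likert means, where the two were level at the extreme ceiling. The claim is therefore confined to mild and moderate skew.
4. **Re-scaling is already permitted and is listed first.** Listing is not ranking. Nothing makes it the default, and elimination is equally allowed.
5. **No bias is shown.** The diagnostic regression may not include arm, and elimination by shape without regard to arm does not itself break FDR control. Both points are accepted. The harm is lost outcomes, lost power and an analysis that cannot be reproduced from the plan.

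Type I error reached 6.2% in one four-point Likert cell, about 2.5 Monte Carlo standard errors above 5%; neighbouring cells gave 5.1% and 4.9%. That supports a robust check, not deletion of the outcome.

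**Conclusion.** The point holds and should be fixed. That the plan offers three unranked responses with no cut point is plain from the text. On the statistics, linear regression of skewed Likert means at 300 or 240 pairs holds type I error near 5%, so non-normality alone does not justify dichotomizing or dropping such an outcome.

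Under the stated assumptions, a median split at skew -0.5 to -1.1 costs 17 to 21 points of power, equivalent to setting aside about 100 to 115 of 300 pairs. A reflected log costs nothing, and elimination forfeits the test.

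The size depends on the assumed effect, correlation, 1:1 allocation and choice of cut. Multiple imputation and differential dropout were not simulated; the n = 240 case is plain loss.

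**What to change.** In both rules, remove dichotomizing and elimination as responses to non-normality, and write instead:

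- Each continuous outcome is analysed by linear regression on its original scale, or on one named transformation fixed before posttest data are examined by arm. A robust standard error or bootstrap interval serves as a check.
- The choice can rest on pooled pretest scores. Study Protocol step 7 opens the assigned resource only after the pretest, so that distribution cannot reflect the program. For example, use a reflected log if pooled pretest skew passes a limit written in the SAP, otherwise the original scale. Pretest shape may not match posttest residuals exactly, which the robust check covers.
- Dichotomized versions are sensitivity analyses only, with a prespecified cut point.
- One arm-blind rule remains for near-constant outcomes, for example 95% or more of pooled responses at one value, reported descriptively. In simulation linear regression still behaved with 96% at the maximum (type I error 4.2%), but beyond that the model could not be fitted in some trials.
- The Benjamini-Hochberg family is fixed before arms are compared, and every outcome is reported.
- If posttest data have already been examined by arm, the SAP says so.

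The cost is SAP wording, with no new data and no change to the regression model. The downsides are that strong-ceiling outcomes stay in the family with low power (about 35% at skew -3.5), and that a transformed outcome is harder to interpret.
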